**Table 10 - Efficacy analyses**

Endpoint	Statistical Analysis Methods
Primary	
IBCFS	Stratified logrank for statistical testing. Stratified Cox proportional hazard model for HR. Kaplan-Meier method for quantiles and probabilities of being event free at different time points.
Secondary	
Key secondary	
IDFS	Stratified logrank for statistical testing. Stratified Cox proportional hazard model for HR. Kaplan-Meier method for quantiles and probabilities of being event free at different time points.
Other secondary	
DRFS, LRRFS, OS	Stratified Cox proportional hazard model for HR. Kaplan-Meier method for quantiles and probabilities of being event free at different time points.
BCSS	Stratified Fine and Gray model for HR. Cumulative incidence function method for quantiles and probabilities of the event of interest at different time points. 1 - Cumulative incidence function method for quantiles and probabilities of being event free at different time points.
Exploratory	Will be described in the SAP.

IBCFS = invasive Breast Cancer-Free Survival; IDFS = invasive Disease-Free Survival; DRFS = Disease Recurrence Free Survival; LRRFS = locoregional recurrences-free survival; HR = hazard ratio; OS = overall survival; BCSS = Breast Cancer-Specific Survival; SAP = statistical analysis plan;

### 9.2.3.3 Other endpoints

#### Patient reported outcomes

Patient reported outcome (PRO) endpoints for the PRO objective will be analyzed in participants from the safety population. These three endpoints are:

- Change from baseline in overall side effect bother as measured by the Functional Assessment of Cancer Therapy Item GP-5 (FACT-GP5).

- Change from baseline in systemic therapy side effects as measured by the EORTC Quality of Life Questionnaire Breast cancer module (EORTC-QLQ-BR23) systemic therapy side effects scale.
- Change from baseline in global health status/quality of life as measured by the EORTC Core Quality of Life Questionnaire (EORTC QLQ-C30) global health status/quality of life (GHQ) scale.

For each questionnaire the compliance profile over time will be summarized on the safety population (number and percentage of forms received versus expected, and number and percentage of forms evaluable versus expected) per treatment arm. Reasons for non-completion will be summarized.

Descriptive statistics on the absolute value and changes from baseline will be done for each treatment arm at each timepoint during treatment period, at EOT, and at the two post-treatment follow up visits will be summarized on the safety population. Between treatment comparisons of the change from baseline over time will be provided for these selected PRO endpoints based on the safety population who have completed the baseline and at least one post-baseline PRO assessment. No formal statistical hypothesis will be tested.

### **Pharmacokinetics**

Pharmacokinetics analyses will be described in the SAP.

#### **9.2.4 Tertiary/exploratory endpoint(s)**

Analysis of tertiary and exploratory endpoints will be described in the SAP.

#### **9.2.5 Safety analysis**

##### **9.2.5.1 Adverse events**

#### **General common rules for adverse events**

The AEs will be analyzed in the following 3 categories:

- Pre-treatment AEs: AEs that developed, worsened or became serious during the pre-treatment period.
- TEAEs: AEs that developed, worsened or became serious during the treatment-emergent period.
- Post-treatment AEs: AEs that developed, worsened or became serious during the post-treatment period.

Similarly, the deaths will be analyzed in the pre-treatment, treatment-emergent and post-treatment periods.

TEAEs will be coded according to MedDRA. Adverse events will be graded according to the NCI-CTCAE v5.0. The grade will be taken into account in the summary. For participants with multiple occurrences of the same preferred term (PT), the maximum grade will be used.

Summaries will be provided for all grades combined and for Grade  $\geq 3$  (including Grade 5). Missing grades, if any, will be included in the “all grades” category.

### **Analysis of all adverse events**

Adverse event incidence table will be provided by treatment group for all types of TEAEs: all TEAEs, all treatment emergent AESI (defined with a PT or a prespecified grouping), all treatment emergent SAEs, all TEAEs related to IMP, all TEAEs leading to permanent treatment discontinuation and all TEAEs leading to dose modification.

The AE summaries will be generated with number (%) of participants experiencing at least one event.

Deaths will also be analyzed.

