### **2.2.2 Early discontinuation and non-adherence to hormonal therapy**

Despite the benefit of adjuvant hormonal therapy (HT) on mortality among women with breast cancer, many women are non-adherent with its use. Hershman et al. investigated the effects of early discontinuation and nonadherence to HT on mortality in women enrolled in Kaiser Permanente of Northern California (KPNC) (1, 11). They identified women diagnosed with hormone-sensitive Stage I–III breast cancer between 1996–2007 and used automated pharmacy records to identify prescriptions and dates of refill. They categorized patients as having discontinued HT early if 180 days elapsed from the prior prescription. For those who continued, they categorized patients as adherent if the medication possession ratio was  $\geq 80\%$ . They used Cox proportional hazards models to estimate the association between discontinuation and non-adherence with all-cause mortality. Among 8769 women who filled at least one prescription, 3802 (43%) received only tamoxifen, while 2313 (29%) received only an AI, and 2654 (30%) received both types of medication. A total of 2761 (32%) discontinued therapy during a median follow-up of 4.5 years: 22% discontinued after AI therapy the first year of treatment. Estimated survival at 10 years was 80.7% for women who continued HT versus 73.6% for those who discontinued ( $p < 0.001$ ). Both early discontinuation and non-adherence to HT were common and associated with increased mortality (1, 11). Currently, the predictors of treatment discontinuation are not clearly defined. Data from the open label, multicenter, randomized ELPh trial showed that 32.4% of the patients treated with AI discontinued the treatment within 2 years because of adverse effects; 24.3% discontinued specifically because of musculoskeletal symptoms. The median time to treatment discontinuation as a result of any symptom was 6.1 months (range, 0.1 to 21.2 months) and the rate of discontinuation within the first year (excluding relapses) was approximately 20%.

The remaining therapeutic options after early discontinuation of an adjuvant AI due to treatment-related toxicities, are either treatment with another AI or tamoxifen. Many patients do not tolerate transition to a different AI and the last option is therefore either tamoxifen or absence of adjuvant therapy.

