## 4 STUDY DESIGN

### 4.1 OVERALL DESIGN

This is a prospective, randomized, international, multicenter, double-blind, double-dummy, Phase 3 study comparing the efficacy and evaluating the safety of amcnestrant *versus* tamoxifen.

The study will have 3 main periods: screening, active treatment, and follow up.

Men, pre/peri-menopausal women (with GnRH analog approved for use in early breast cancer) and post-menopausal women with HR+ early breast cancer, who have discontinued adjuvant AI therapy due to treatment-related toxicity will enter the screening period to assess their eligibility.

**Participants still on AI treatment may enter the screening period for central confirmation of biomarkers and screening imaging assessments. The other assessments/questionnaires required before randomization will be performed/completed when patient is off the AI therapy.**

All eligible participants for whom ER and PgR status have been centrally confirmed will be randomly assigned using an IRT to either amcnestrant 200 mg daily (experimental) arm or tamoxifen 20 mg daily (control) arm in a 1:1 ratio.

- Arm A: Amcnestrant 200 mg + tamoxifen-matching placebo
- Arm B: Amcnestrant-matching placebo + tamoxifen 20 mg

All randomized patients will also receive the matching placebo of the other treatment under evaluation. Both treatments are given orally.

The study population will be stratified by the following factors, as reported at the time of randomization:

- Prior exposure to (neo)adjuvant AI therapy:  $\leq 12$  months vs.  $> 12$  months
- Prior exposure to (neo)adjuvant chemotherapy and HER2 status: HER2-negative breast cancer with NO prior (neo)adjuvant chemotherapy vs. HER2-negative breast cancer with prior (neo)adjuvant chemotherapy vs. HER2-positive breast cancer with prior (neo)adjuvant chemotherapy

Note: Participants with unknown HER2 status will be classified as HER2-negative.

- Prior exposure to CDK4/6 inhibitor (Yes or No)
- Geographic regions (North America, Europe vs. Asia Pacific vs. Other)
- Men or peri-/pre-menopausal women vs. post-menopausal women

During the treatment period, men and pre/perimenopausal women will receive GnRH analogs as approved in the respective countries.

Participants will receive their assigned treatment for the planned duration of 5 calendar years or until diagnosis of disease recurrence per IBCFS definition or any other withdrawal criterion whichever occurs first.

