Early discontinuation during the active study treatment period will be left at the investigator's discretion.

Extended adjuvant endocrine therapy upon completion of study treatment is allowed, but treatment will not be provided by the sponsor. Treatment recommendation should be considered on an individual patient basis taking into consideration clinico-pathologic characteristics, patient's preferences, and total duration of adjuvant endocrine therapy at the time of study treatment completion or discontinuation. When extended adjuvant endocrine therapy is considered, treatment options include adjuvant tamoxifen or adjuvant aromatase inhibitor.

In case of diagnosis of second non-breast primary invasive cancers, the decision to keep the patient on protocol treatment is based on clinical judgement of the treating physician. Patients diagnosed with a second primary malignancy not requiring systemic therapy (ie, chemotherapy, hormonal therapy, targeted therapy, etc) and with no evidence of breast cancer recurrence may continue with study drug treatment according to the protocol and schedule of assessment, if considered by the investigator to be in the patient's best interest, whenever possible. Study treatment may be temporarily suspended to allow for local treatment (surgery and/or radiation) of the second non-breast primary invasive cancer; in this situation, the maximally allowed period of protocol treatment discontinuation should not exceed a total of 3 months in any 12-month time period.

Participants discontinuing or completing the active study treatment period will be followed up to 10 years from randomization, except in case of premature study termination due to one of the following reasons: withdrawal of consent, loss to follow-up or death.

An IDMC will monitor the safety data on a periodic basis. The IDMC will make recommendations as to whether the trial should continue based on ongoing reviews of safety data. The IDMC will also evaluate efficacy at the interim analyses and make a recommendation regarding study continuation based on observed results of the current study and/or external study data generated with amcnestrant. The IDMC procedures will be described in the full protocol and detailed in the IDMC charter and will be approved by IDMC members.

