**Table 6 - Populations for analyses**

Population	Description
Screened	All participants who signed the ICF.
Randomized	All participants from screened population who have been allocated to a randomized intervention by IRT regardless of whether the intervention was received.
Intent-to-treat (ITT)	All randomized participants. Participants will be analyzed according to the intervention allocated by randomization.
Safety	All randomized participants who took at least 1 dose of study intervention. Participants will be analyzed according to the intervention they actually received.
PK population	All randomized and treated participants (safety population) with at least one post-baseline PK concentration with adequate documentation of dosing and sampling dates and times. Participants will be analyzed according to the intervention they actually received.

Participants exposed to study intervention before or without being randomized will not be considered randomized and will not be included in any analysis population. The safety experience of these participants will be reported separately.

Randomized participants for whom it is unclear whether they took the study intervention will be considered as exposed and will be included in the safety population as randomized.

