#### 9.2.1 General considerations

The baseline value is defined as the last available value before randomization, unless otherwise specified.

Unless otherwise specified, analyses will be performed by intervention group (and overall for baseline and demographics characteristics).

The observation period will be divided into 3 segments:

- The **pre-treatment period** is defined as the period up to first IMP administration.

- The **on-treatment period** (ie, treatment-emergent (TE) period) is defined as the period from the first IMP administration to the last IMP administration + 30 days.
- The **post-treatment period** is defined as the period from the end of the on-treatment period.

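### Adverse events are summarised only as crude percentages over an on-drug window, so unequal discontinuation could distort the arm contrast for events that accrue over time

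*Combined protocol and SAP*

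**What the plan says.** Section 9.2.5.1 plans incidence tables by treatment group for all TEAEs, AESIs, SAEs, related TEAEs, and TEAEs leading to discontinuation or dose modification. The measure is fixed: "The AE summaries will be generated with number (%) of participants experiencing at least one event". The denominator, in Table 6, is "All randomized participants who took at least 1 dose of study intervention". The window in Section 9.2.1 runs "from the first IMP administration to the last IMP administration + 30 days".

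Time on drug varies between participants. Section 4.1 sets the plan: "Participants will receive their assigned treatment for the planned duration of 5 calendar years", or "until diagnosis of disease recurrence per IBCFS definition" or another withdrawal criterion. It adds: "Early discontinuation during the active study treatment period will be left at the investigator's discretion".

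The protocol mentions no person-year rate, time-to-first-event analysis or cumulative incidence for AEs. Section 9.2.5.1 treats post-treatment AEs as a separate category. Section 8.3.1 requires new AEs arising more than 30 days after the last dose to be reported only if related. Section 9.2 defers further detail to an SAP whose text is not among the documents.

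**The concern.** Randomisation balances the arms at entry but not their time on drug afterwards. When the window closes shortly after drug stops, the arm that stops earlier has less time to record an event. At the same event rate it shows a lower percentage, and at a higher true rate it may show the same one.

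Unequal stopping is plausible here. Everyone enrolled has already given up an aromatase inhibitor for toxicity, and stopping is discretionary. Section 2.2.2 cites a hormonal-therapy cohort in which "A total of 2761 (32%) discontinued therapy during a median follow-up of 4.5 years". Drug also stops at recurrence, so the design HR of 0.76 by itself implies slightly longer exposure on amcenestrant.

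What is at stake is the reading of a stated secondary objective, safety in both arms. The events most exposed to the problem are those that accrue on drug. Table 1 names uterine malignancy and thromboembolism for tamoxifen, and a theoretical long-term risk of osteoporosis for amcenestrant.

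**Working it through.** **Inputs from the protocol.** Table 12 enrols 5%, 10%, 25% and 60% of participants in months 0-3, 3-6, 6-12 and 12-24. The final cut-off is month 60, with 1869 participants per arm. Follow-up f is 60 months minus entry, so it is 36 to 60 months and the 5-year treatment cap never binds. Mean f = 0.05×4.875 + 0.10×4.625 + 0.25×4.25 + 0.60×3.5 = 3.87 years.

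**Check of the accrual model.** The AE section states no figure of its own. The same accrual with exponential event times, 82% four-year IBCFS on tamoxifen, HR 0.76 and 1% annual dropout gives 189, 427 and 568 events at months 28, 47.5 and 60. Table 11 has 189, 426 and 568, so the follow-up pattern is right.

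**Assumed inputs (not in the documents).** A constant AE hazard h, identical in both arms, and a constant discontinuation hazard d that differs by arm. For scale, 32% stopping over a median 4.5 years is roughly −ln(0.68)/4.5 = 8.6% per year in the cited cohort. That supports the level of d, not any difference between arms.

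**Formulas, averaged over accrual.**
- Mean exposure = (1 − exp(−d·f))/d
- Crude percentage = h/(h+d) × (1 − exp(−(h+d)·f))

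**Hand check at f = 3.87, h = 0.5% per year.**
- d = 8%: exposure (1 − e^−0.310)/0.08 = 3.33 years; crude 0.005/0.085 × (1 − e^−0.329) = 1.65%
- d = 16%: exposure (1 − e^−0.619)/0.16 = 2.88 years; crude 0.005/0.165 × (1 − e^−0.639) = 1.43%

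**Averaged over Table 12.** Exposure is 3.32 vs 2.87 years and the crude percentages are 1.64% vs 1.42%, a ratio of 1.16 although the hazards are equal.

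| Discontinuation per year | Spurious ratio, h = 0.5-10% per year |
|---|---|
| equal | 1.00 (no artefact) |
| 8% vs 12% | 1.07-1.08 |
| 8% vs 16%, h = 0.5% | 1.16 |
| 10% vs 20% | 1.18-1.19 |

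Adding the 30-day tail lowers 1.16 to 1.15. Reading d as annual probabilities gives 1.08-1.23.

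**Masking.** For a rare event the true ratio that can be hidden is about the exposure ratio, 3.32/2.87 = 1.16. A second calculation used annual probabilities, the 30-day tail and AE rates of 2 and 5 per 100 participant-years. Crude percentages were equal when the shorter-exposure arm's true rate was 1.10-1.11 times higher (5% vs 10% stopping) or 1.22-1.23 times higher (10% vs 20%). An extreme 5% vs 22% gave 1.41-1.42.

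**Exposure gap from efficacy alone.** Treating every IBCFS event as stopping drug, mean exposure is 3.60 years on amcenestrant and 3.51 on tamoxifen, a ratio of about 1.03.

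**Where the person-year rate fails.** Assume 20% of participants are susceptible, with mean onset at 2 months, and stopping of 5% vs 22% per year. Crude percentages are 19.8% vs 19.5%, close to the truth. Person-year rates are 6.95 vs 9.52 per 100, a false difference.

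**The case against.** The strongest reply is that nothing here is an error. On-treatment n (%) is a legitimate description, no between-arm AE test is planned, and no type I error or sample size depends on it. Section 9.2 calls itself a summary, and the SAP could still add rates. All of that stands. It makes this an improvement to the plan, although the protocol does state a concrete measure and promises no exposure adjustment.

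The imbalance is also assumed. No passage gives discontinuation by arm, and the cited cohort is not randomised. A reader might infer that the arms will differ and the safety tables will be biased; the documents do not support that.

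The rare-event example is small in absolute terms: 1.64% vs 1.42% of 1869 is about 31 vs 27 participants, and a nominal 95% CI would exclude zero in only about 8.5% of trials. The gap is more visible for commoner accruing events, about 15.2% vs 13.2% at 5% per year.

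Some named risks are partly followed past drug stop. A second non-breast primary cancer is an IDFS event, analysed by ITT irrespective of discontinuation (Table 9), though as a first event and not specifically uterine. Bone densitometry continues every 2 years to the end of follow-up (Section 1.3). New related AEs are still collected. None of this gives equal follow-up for unrelated AEs or replaces the AE tables.

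A reader might also infer that staggered entry (36 to 60 months of follow-up) adds bias. It does not, because entry date is balanced by randomisation.

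**Conclusion.** The point holds as a conditional one. For events that accrue during treatment, the stated measure mixes event rate with time on drug. If annual discontinuation differs by 8% vs 12% up to 10% vs 20%, equal hazards yield a crude ratio of about 1.07 to 1.19, and true excesses of similar size can be hidden. This rests on constant hazards, Table 12 accrual, a month-60 cut-off and an assumed arm difference. With equal discontinuation the artefact disappears, and for early-onset events it is negligible.

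The tempting stronger conclusion, that person-year rates should replace percentages for all safety statements, is not supported. They mislead for early-onset events, and for TEAEs leading to discontinuation the event itself ends the exposure. Adding the rates is a cheap improvement, best specified before unblinding so that the safety metric is not chosen after the results are seen.

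**What to change.** In Section 9.2.5.1 or the SAP, keep every n (%) table and add, by arm:

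- Duration of exposure.
- For SAEs, AESIs, uterine malignancy, thromboembolism and osteoporosis: participants with a first event per 100 participant-years at risk, with the rate difference and 95% CI.
- Ideally, cumulative incidence of first event, with drug stop and death as competing events. This shows timing but still reflects how long participants stay on drug, so read it beside the exposure summary and the rates.

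State that between-arm differences in accruing events are read with these measures, and that statements on early-onset AEs, all TEAEs or TEAEs leading to discontinuation do not rest on person-year rates alone.

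The cost is a few more tables. Dosing dates are already recorded in the CRF (Section 6.4). The downside is that constant-rate summaries are uninformative for early-onset events, which is why the percentages stay.

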### **9.2.5.2 Laboratory variables, vital signs and electrocardiograms (ECGs)**

#### **Analyses according to PCSA and NCI grading**

For laboratory variables, analyses according to NCI grading will be made based on NCI-CTCAE version 5.0. In addition, for laboratory variables for which NCI-CTCAE scale is not applicable, vital signs and ECG variables, PCSA analyses will be performed based on the PCSA list currently in effect at Sanofi at the time of the database lock.

Analyses according to PCSA and NCI grading will be performed based on the worst value during the treatment-emergent period, using all measurements (either local or central, either scheduled, nonscheduled or repeated).

For laboratory variables, vital signs and ECG variables, the incidence of participants with at least one PCSA during the treatment-emergent period will be summarized regardless of the baseline level and according to the following baseline status categories:

- Normal/missing
- Abnormal according to PCSA criterion or criteria

For laboratory variables graded by NCI-CTCAE.

- The number (%) of participants with abnormal laboratory tests at baseline will be presented by grade.
- The number (%) of participants with abnormal laboratory tests during the treatment-emergent period will be summarized by grade. When appropriate, the number (%) of participants with abnormality of any grade and with Grade 3-4 abnormalities will be provided.

For ECG, the incidence of participants with at least one abnormal ECG during the treatment-emergent period will be summarized regardless of the baseline level and according to the following baseline status categories:

- Normal/missing
- Abnormal

